5.6 Packaging and Labeling

The study drugs will be supplied in wallet cards containing 2 S-033188 active 20-mg tablets or its matching placebo with/without the 10 oseltamivir capsules or their matching placebo, or only placebo. The wallet card will be labeled with an identification number, protocol number, contents, direction for use, storage condition at a minimum, as well as other pertinent information according to local regulations. The expiry or use by date will be stored in the IWRS or on the label according to local regulations. Study drug should not be used after the expiry or use by date. All packaged and labeled supplies will be formally released in accordance with both Good Manufacturing Practice (GMP) and Good Clinical Practice (GCP) guidelines.

5.7 Storage and Accountability

The study drug will be stored at room temperature (15°C to 25°C [59°F to 77°F]). The temperature of the drug storage area will be recorded every working day.

The investigator or person responsible for study drug handling will ensure that all study drugs are stored and dispensed in accordance with local regulations concerning the storage and administration of investigational drugs. All drug supplies must be kept in a secure locked area with access limited to those authorized by the investigator.

The investigator or pharmacist will maintain accurate records on the following information: receipt and condition of all study drugs, date of the receipt, when and how much study drug is dispensed and used by each patient in the study, and any reasons for departure from the protocol-dispensing regimen. The drug accountability records will be available for verification by the sponsor's monitor (or designee) at each monitoring visit. At the completion of the study, a final reconciliation of all study drugs will be performed. Study drug must not be used for any purpose other than the present study. Further details on drug procedures and accountability are described in a separate written procedure.

5.8 Investigational Product Retention at Study Site

At the end of the study, all unused study drug and used wallet cards will be returned. The site monitor or designee responsible for study drug handling will record accurate amounts of used and unused drug supplies. Final reconciliation must be completed by the monitor prior to returning. All used and unused drug supplies in appropriate boxes will be returned as per the sponsor's written instructions with a copy of the overall drug accountability record and appropriate return form as described in a separate written procedure.

5.9 Treatment Compliance

The investigator or subinvestigator will administer the first dose of the study drugs and perform a mouth check of patients immediately after the drug is taken. The time of ingestion (coadministration of S-033188, oseltamivir, and placebo) will be recorded in the source documents and the eCRFs. Patients must bring their tablet cards and any unused drug at all visits up to Visit 5 (Day 9), unless dosing was completed at Visit 4 (Day 5), whether or not the tablet card is empty. The investigator or subinvestigator will review the tablet cards to verify that the correct number of doses has been taken according to the actual time interval that has elapsed between clinic visits. A record of the supplies dispensed and returned will be documented. Based on compliance checks, if < 100% of the required study drug has been taken by a patient, the patient will be counseled by the site about the importance of taking the study drugs as directed.

6. RESTRICTIONS

6.1 **Prior Therapy**

Prior therapies are defined as therapies that were taken prior to the initiation of study treatment. All prior therapy (prescription drugs, over-the-counter drugs, procedures without any medication) taken by a patient within 14 days prior to the initiation of study treatment will be recorded in the eCRF, and the information will include a name of used drug or used procedures, duration of treatment, and reason for use.

6.2 Concomitant Therapy During the Study

Concomitant therapies are defined as therapies taken at or after the initiation of study treatment. The investigator or subinvestigator will record the following information for all therapies (prescription drugs, over-the-counter drugs, procedures without any medication) used during the study (from Visit 1 [Day 1] to Visit 7 [Day 22] or ET) in the eCRF.

- Name of used drug or used procedures
- Route of administration
- Duration of treatment
- Reason for use

6.2.1 Prohibited Concomitant Therapy

The use of the following drugs and over-the-counter drugs with equivalent efficacy to them will be prohibited from Visit 1 (Day 1) until Visit 7 (Day 22) or ET.

- Systemic antiviral drugs (excluding antiretrovirals for the treatment of HIV infection or herpes simplex virus (HSV) suppressive therapy)
- Antimicrobial* and antifungal drugs**
- Antipyretics/analgesics except provided acetaminophen/paracetamol***
- Antitussives and expectorants
- Combination cold remedies
- Antihistamines**
- Herbal medicines or complementary therapies indicated for influenza virus infection (eg, Maoutou)
- Other investigational drugs
- * Except for the treatment of complications of influenza suspected to be bacterial infection after Day 1.
- ** Dermal preparations will be permitted, but application to the eyes, nose, and ears or by inhalation will be prohibited.
- *** Low dose aspirin for cardiovascular disease prophylaxis will be acceptable.

6.2.2 Rescue Therapy (Noninvestigational Product)

If influenza symptoms, such as fever, headache, and muscle pain, are so severe that the patient needs rescue therapy between Visits 1 (Day 1) and 7 (Day 22), the use of acetaminophen or paracetamol at a dose of 3000 mg/day or less will be permitted only for the relief of fever or pain. The site can supply the acetaminophen/paracetamol tablets or the investigator can prescribe the tablets then reimburse the patient; in either case, the country's commercial pack will be used, and the sponsor or designee will indirectly supply the tablets by reimbursing the site. If acetaminophen/paracetamol is used, the patient will record the date and time of each administration in the patient eDiary. The measurement of body temperature and assessment of influenza symptoms by the patient will occur immediately before the use of acetaminophen/paracetamol or more than 4 hours after acetaminophen/paracetamol administration.

6.3 Other Restrictions

6.3.1 Contraception

Women of childbearing potential (WOCBP) should use 1 of the following highly effective methods of contraception as instructed by the investigator or subinvestigator for 3 months after the initiation of the study treatment (Visit 1, Day 1).

Highly effective methods of contraception are:

- Combined (estrogen and progestogen containing) hormonal contraception associated with inhibition of ovulation:
 - Oral
 - Intravaginal
 - Transdermal
- Progestogen-only hormonal contraception associated with inhibition of ovulation:
 - Oral
 - Injectable
 - Implantable
- Intrauterine device (IUD)
- Intrauterine system (IUS, ie, Mirena[®])
- Bilateral tubal occlusion
- Vasectomized partner
- Sexual abstinence (considered a highly effective method only if defined as refraining from heterosexual intercourse during the entire period of risk associated with the study treatments; the reliability of sexual abstinence will need to be evaluated in relation to the duration of the clinical trial and the preferred and usual lifestyle of the patient)

7. STUDY PROCEDURES AND METHODS OF ASSESSMENTS

The time and events schedule is included in Appendix 1.

7.1 Informed Consent

The investigator or subinvestigator will fully explain the nature of the study to a patient and parent(s)/legally acceptable representative using the Institutional Review Board (IRB)/Independent Ethics Committee (IEC)-approved informed consent document. When the patient agrees to participate in the study, the patient must voluntarily sign a consent form prior to the initiation of any study procedures. A copy of the signed and dated informed consent document will be given to the patient. The signed and dated original consent form will be retained by the investigator. Informed consent will be obtained from all patients. A patient cannot be entered the study until he/she has signed and dated on the consent form.

The investigator or subinvestigator is responsible for ensuring that the patient understands the risks and benefits of participating in the study, including answering any questions the patient may have throughout the study and sharing any new information in a timely manner that may be relevant to the patient's willingness to continue his/her participation in the study.

The investigator or subinvestigator will fully explain the nature of the study to a patient and parent(s)/legally acceptable representative as required by age or local regulations of each patient by using the IRB/IEC-approved informed consent/assent document. Informed consent will be obtained from parent(s) or legally acceptable representative of each patient. The parent or the legally acceptable representative must sign a consent form prior to the initiation of any study procedures. Patients will be informed about the nature and duration of the study with written age-appropriate information, in language and terms they can understand and must sign an assent form. A copy of the signed and dated informed consent/assent document will be given to the patient and parent(s)/legally acceptable representative. The signed and dated original consent/assent form will be retained by the investigator. Informed consent will be obtained from parent(s)/legally acceptable representative of all patients. A patient cannot be entered the study until his/her parent(s)/legally acceptable representative has signed and dated the consent form.

7.2 Baseline Patient Characteristic and Medical History

The following baseline patient characteristics will be obtained at Visit 1 (Day 1) if allowed per the country's requirement and entered in the eCRF: preexisting date of written informed consent by the patient/guardian, date of birth, sex, ethnicity, race, current smoking status, prior therapy, and medical history. Medical history will include any previous medical condition requiring hospitalization, all concurrent medical conditions, surgical history (within 12 months), presence or absence of influenza vaccination within the last 6 months, and duration of influenza symptoms.

7.2.1 Rapid Influenza Diagnostic Test (RIDT)

Once a patient has been determined to be eligible based on body temperature and clinical symptoms, the investigator or subinvestigator will collect nasopharyngeal (a nasopharyngeal swab is preferred, but a pharyngeal swab will be acceptable if a nasopharyngeal swab cannot be performed) swabs for influenza A and/or B virus using a supplied commercial RIDT kit at the same time as performing the central lab PCR nasopharyngeal/pharyngeal swabs. The RIDT results will be recorded in the eCRF. The collection of specimens, operation of the kit, and interpretation of test results will be performed according to the instructions for use or package insert of the RIDT kit. The RIDT will be provided by the sponsor, and this will be the preferred test; however, if a site has performed a RIDT prior to consideration for the study, the local RIDT result will be entered into the eCRF. The patient will be informed of the RIDT result, and if the result is negative, the investigator will explain the low and unpredictable sensitivity of the RIDT and will confirm with the patient that they wish to continue in the study. This decision will be documented in the ICF addendum, and this will serve as source documentation.

7.2.2 Meals

To collect information on meals before and after the initial study treatment (coadministration of S-033188, oseltamivir, and placebo), whether the patient takes meals on Day 1 and the time of meal ingestion will be recorded in the eCRF.

7.3 Enrollment in the Study and Dispensing Study Drug

After a patient is determined to be eligible according to the inclusion/exclusion criteria, the investigator or subinvestigator will contact the Interactive Response Technology (IRT) for an identification number or send the registration sheet with the required information filled in to the registration center. If the registration is accepted, the patient will be entered in the study. After the patient is entered in the study, the investigator, subinvestigator, or site pharmacist will dispense the study drug as specified in Section 5.

7.4 Efficacy Assessments

7.4.1 Patient Electronic Diary

The patient will self-measure/assess the following outcome measures and record the results in the patient electronic diary (eDiary). The patient eDiary will consist of electronic data entered by the patient into the electronic patient-reported outcome (ePRO) system via a mobile computer or other vendor-provided electronic devices.

The results of the measurements and assessments will be entered into the eDiary predose at Visit 1 (Day 1) once the device has been set up by the investigator or designee. After the initiation of the study treatment on Day 1, only the measurements and the assessments in the available time period of the day will be conducted. If the study treatment is initiated at 18:00 or later on Day 1, the patient will not need to perform Day 1 evening assessments.

Prior to the initiation of the study treatment on Day 1, the investigator, subinvestigator, or study coordinator will instruct the patient on how to assess the outcome measures and then have him/her record the results of the initial assessments. The ePRO system will be personally delivered to the patient after enrollment.

7.4.1.1 Body Temperature Measurement

With an electronic thermometer, the patient will self-measure axillary temperature. The sweat should be wiped off the measurement site in advance. The patient will measure and record in the patient eDiary, body temperature predose on Day 1, and then 4 times daily (morning, noon, evening, and bedtime) until Day 3 and twice daily (morning and evening) from Days 4 to 14. With Table 7-1 as a guide, the patient will measure body temperature when it is possible to do so. After the initiation of the study treatment, body temperature measurement will occur before taking acetaminophen or more than 4 hours after the last dose of acetaminophen.

The body temperature obtained at the study center prior to informed consent will be acceptable as an alternative to the predose value on Day 1 (provided that it is obtained on Day 1).

Assessment Period	Time Period of a Day	Time Window as a Guide
Assessment renou	Time reflot of a Day	Time window as a Guide
Days 1 to 3	Morning	- 9:59
	Noon	10:00 to 14:59
	Evening	15:00 to 19:59
	Bedtime	20:00 -
Days 4 to 14	Morning	- 11:59
	Evening	18:00 -

Table 7-1 Time Windows of Body Temperature Measurement as a Guide

7.4.1.2 Assessment of Severity of Influenza Symptoms

The patient will self-assess 7 symptoms associated with influenza (cough, sore throat, headache, nasal congestion, feverishness or chills, muscle or joint pain, and fatigue) on a 4-point rating scale (0, None; 1, Mild; 2, Moderate; 3, Severe).

The patient will assess and record on a paper questionnaire, influenza symptoms predose on Day 1; then subsequent influenza symptoms will be assessed and recorded in the patient eDiary twice daily (morning and evening) until Day 9, and once daily (evening) from Days 10 to 14. Table 7-2 provides the time windows of assessment as a guide.

18:00 -

of Severity of Influenza Symptoms		
Assessment Period	Time Period of a Day	Time Window as a Guide
Days 1 to 9	Morning	- 11:59
	Evening	18:00 -

Evening

Table 7-2 Time Windows of Assessment as a Guide: Assessment

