The required sample size will therefore be calculated based on the conservative assumption of a 36-hour difference (assuming that the median time to improvement of influenza symptoms in the placebo group and the S-033188 group was 150 and 114 hours, respectively) in the median time to improvement of influenza symptoms between the S-033188 group and the placebo group to ensure at least 90% power in the efficacy evaluation of S-033188.

Patients will be randomized on a 1:1 basis to either S-033188 or placebo and a follow-up period will be 336 hours (14 days). Assuming that the time follows an exponential distribution, the study will require 790 patients in the ITTI population in order for the generalized Wilcoxon test to have 90% or more power with a 2-sided significance level of 5% (395 patients in the S-033188 group and placebo group, respectively).

Using a 1:1 randomization ratio between the S-033188 group and the oseltamivir group, the ITTI population of oseltamivir will be 395 patients. Table 9-1 shows the statistical power to compare between the S-033188 group and the oseltamivir group under several sets of assumed time to improvement of influenza symptoms.

Table 9-1	Statistical Power to Compare Between S-033188 and
	Oseltamivir

Median Time to Alleviation of Symptoms (S-033188, Oseltamivir)	Statistical Power for Comparison Between S-033188 and Oseltamivir by Generalized Wilcoxon Test
(114 hours, 126 hours)	22.3%
(108 hours, 126 hours)	45.3%
(102 hours, 126 hours)	71.5%
(96 hours, 126 hours)	90.2%

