9.10.1 Primary Efficacy Endpoint Analyses

The primary efficacy endpoint will be the time to improvement of influenza symptoms (with modification for preexisting symptoms):

- Preexisting symptoms (ie, cough, fatigue, or muscle/joint pain that existed prior to developing influenza) that were judged by the patient to be worse at baseline (ie, the predose examinations) must improve from baseline severity
 - o Improvement in baseline severity is as follows:
 - Severe \rightarrow moderate, mild, or absent
 - Moderate \rightarrow mild or absent
 - Note: At baseline (ie, the predose examinations), patients will only be asked if
 preexisting symptoms existed (within the last 30 days) and if they were
 worsened by influenza. Patients will be asked to rate the severity at baseline
 that is the severity that needs to improve. To avoid recall bias, patients will
 not be asked to rate the severity of preexisting symptoms prior to influenza.
- Preexisting symptoms (ie, cough, fatigue, or muscle/joint pain that existed prior to developing influenza) that were judged by the patient to NOT be worse at baseline (ie, the predose examinations) must have their baseline severity maintained

- o Maintenance of baseline severity is as follows:
 - Severe \rightarrow Severe
 - Moderate \rightarrow Moderate
- For new symptoms at baseline (ie, the predose examinations), alleviation of symptoms assessment will not be modified
 - Alleviation of symptoms is as follows:
 - Severe \rightarrow mild or absent
 - Moderate \rightarrow mild or absent

Once all of a patient's influenza symptoms are alleviated, maintained, or improved as defined above, the endpoint for that patient will be reached, for a duration of at least 21.5 hours (24 hours – 10%).

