9.10.2 Secondary Efficacy Endpoints

The secondary efficacy endpoints include the following variables.

1) Proportion of patients positive for virus titer and proportion of patients positive by RT-PCR at each time point

Defined as the percentage of patients whose virus titer is not < the lower limit of quantification among those assessed for virus titer, and the percentage of patients with detectable virus RNA among assessed by RT-PCR, respectively.

2) Change from baseline in virus titer and in the amount of virus (RT-PCR) at each time point

Defined as the change from baseline in virus titer and the change from baseline in the amount of virus RNA, respectively. Baseline is defined as the last value obtained before the initial dose.

3) AUC adjusted by baseline in virus titer and in the amount of virus RNA (RT-PCR)

Defined as AUC, where AUC is the area under the curve, of change from baseline in virus titer and AUC of change from baseline in the amount of virus RNA, respectively. AUC is calculated using the trapezoidal method.

4) Time to cessation of viral shedding by virus titer and by RT-PCR

Defined as the time between the initiation of the study treatment and first time when the virus titer is < the lower limit of quantification and the time between the initiation of the study treatment and first time when virus RNA by RT-PCR is < the lower limit of quantification, respectively.

5) Proportion of patients whose symptoms has been alleviated at each time point

Defined as the percentage of patients whose primary endpoints are improved after the initiation of the study treatment in the analysis population by each time point. 6) Time to alleviation of symptoms (cough, sore throat, headache, nasal congestion, feverishness or chills, muscle or joint pain, and fatigue)

Defined as the time between the initiation of the study treatment and the alleviation of influenza symptoms. The alleviation of influenza symptoms is defined as the time when all of 7 influenza symptoms have been assessed by the patient as 0 (None) or 1 (Mild) in the patient eDiary, for a duration of at least 21.5 hours (24 hours -10%).

7) Time to improvement in the 4 systemic symptoms (headache, feverishness or chills, muscle/joint pain, and fatigue)

Defined as the time between the initiation of the study treatment and the improvement in the 4 systemic symptoms. The assessment follows the criteria for the primary endpoint.

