c The patient will measure or assess and record in the patient diary, body temperature 4 times daily (morning, noon, evening, and bedtime) from Days 1 to 3 and twice daily (morning and evening) from Days 4 to 14; assessment of health once daily (evening) from Days 1 to 14; the severity of influenza symptoms twice daily (morning and evening) from Days 1 to 9 and once daily (evening) from Days 10 to 14; and the CPI twice daily (morning and evening) from Days 1 to 9 and once daily (evening) from Days 2 or ET.

d Predose; if the study treatment is initiated at 18:00 or later on Day 1, the patient will not need to perform the Day 1 evening assessments.

e Including measurement of body weight.

f Height and body mass index will be measured at the predose examinations only.

g Urine pregnancy test will be performed only for females who are not diagnosed as postmenopausal.

h Predose.

i To be collected if the investigator determines that flu symptoms are persisting.

j If the investigator determines that flu symptoms are persisting at ET.

k Blood samples will be collected for the measurement of plasma drug concentrations once each at Visits 2 (Day 2) and 4 (Day 5). If circumstances permit, samples also will be collected within the period from 0.5 to 4 hours after the initial dose at Visit 1 (Day 1), at Visit 3 (Day 3), and at Visit 6 (Day 15).

Quality-of-Life Questionnaire Appendix 2

CPI

Study center name	
Patient identification code	
Visit	
Date	

Under each heading, please tick the ONE box that best describes your health TODAY.

CPI

CPI

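### Section 9.2 sizes the trial on 336 hours of follow-up, but the symptom diary ends with the Day 14 evening entry, before 336 hours, so the stated 90% power is narrowly missed

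*Protocol*

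**What the plan says.** - Protocol Section 7.4.1.2: after twice-daily entries to Day 9, symptoms are scored "once daily (evening) from Days 10 to 14". Appendix 1, footnote c, repeats the schedule: "the severity of influenza symptoms twice daily (morning and evening) from Days 1 to 9 and once daily (evening) from Days 10 to 14". Visits 6 (Day 15) and 7 (Day 22) follow, but no patient symptom scoring is scheduled at them.
- Section 7.4.1.2 on clock times: "Table 7-2 provides the time windows of assessment as a guide". The evening window opens at 18:00 and has no stated end.
- Section 7.4.1 sets no fixed dosing time and provides for late dosing: "If the study treatment is initiated at 18:00 or later on Day 1", the Day 1 evening assessments are dropped.
- Section 9.10.1: the improved state must hold "for a duration of at least 21.5 hours".
- Section 9.10.2 gives the time origin for the parallel alleviation endpoint: "Defined as the time between the initiation of the study treatment and the alleviation of influenza symptoms".
- Section 9.2 sizing basis: "a follow-up period will be 336 hours (14 days", exponential times, a two-sided 5% generalized Wilcoxon test, 395 infected patients per arm, at least 90% power, and medians "in the placebo group and the S-033188 group was 150 and 114 hours, respectively".

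**The concern.** The sizing rests on a follow-up that the diary does not deliver. Day 14 is the fourteenth calendar day, counted from a Day 1 that already contains the dose, so an entry that evening lies roughly 13 × 24 h after dosing. From Day 10 the entries are one evening apart. An improvement first recorded on the evening of Day 14 therefore has no later entry to show that it lasted 21.5 hours.

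At stake is whether the stated power holds on the protocol's own schedule, and whether Section 9.2 and the diary schedule describe the same observation window. Both are fixed in the protocol, so a statistical analysis plan could not make them agree.

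**Working it through.** **Inputs.** From Section 9.2: medians of 150 h (placebo) and 114 h (S-033188), exponential times, 395 per arm, two-sided 5%, follow-up T = 336 h. Assumed, because the protocol does not give them: dose at 08:00–20:00 on Day 1, evening entry at 18:00–24:00, and consecutive evening entries about 24 h apart.

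**1. Reproduce the plan's figure.** Hazards are λ₁ = ln 2/114 = 0.006080 and λ₀ = ln 2/150 = 0.004621 per hour. For the Gehan (generalized Wilcoxon) statistic with administrative censoring at T and n per arm:

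- A = (λ₁ − λ₀)/(λ₁ + λ₀) × [1 − exp(−(λ₁ + λ₀)T)]
- B = λ₁/(2λ₁ + λ₀) × [1 − exp(−(2λ₁ + λ₀)T)] + λ₀/(λ₁ + 2λ₀) × [1 − exp(−(λ₁ + 2λ₀)T)]
- z = √n × A/√B, and power = Φ(z − 1.960)

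At T = 336: A = 0.1326, B = 0.6609, z = 19.87 × 0.1326/0.8129 = 3.242, power = Φ(1.282) = 90.01%. With 394 per arm it is 89.94%. So 395 is the smallest number that reaches 90%, and there is no reserve. The same formula gives 22.2, 45.3, 71.5 and 90.2% for Table 9-1, against the printed 22.3, 45.3, 71.5 and 90.2%. A log-rank calculation would give 337 per arm and does not match. This identifies 336 h as the follow-up behind both the sample size and Table 9-1.

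**2. What the diary can observe.**

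- Last entry (Day 14 evening) = 13 × 24 + (entry time − dose time). Lowest: 312 + 18 − 20 = 310 h. Highest: 312 + 24 − 8 = 328 h.
- Event dated to the start of the spell: the last onset that can be confirmed is the Day 13 evening entry, 24 h earlier, at 286–304 h.
- Event dated to the end of the spell: the limit is the last entry itself, 310–328 h.

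A 22:00 dose with an 18:00 entry would lower the first range to 284 h. A Day 14 entry made less than 21.5 h after the Day 13 entry would not confirm a Day 13 onset at all, which is why entries about 24 h apart are assumed.

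**3. Power on that window, 395 per arm.**

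| Follow-up | z | Power |
|---|---|---|
| 336 h | 3.242 | 90.0% |
| 328 h | 3.235 | 89.9% |
| 310 h | 3.217 | 89.6% |
| 304 h | 3.210 | 89.4% |
| 286 h | 3.187 | 89.0% |

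Reaching 90% at 304 h or 286 h would take 403 or 409 per arm, that is 8 to 14 more. At 298 h the last row of Table 9-1 moves from 90.2% to about 89.7%.

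**4. Events beyond the window**, taking 298 h as an example and dating to the start of the spell:

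- Placebo: exp(−λ₀ × 298) − exp(−λ₀ × 336) = 0.252 − 0.212 = 0.041, about 16 of 395.
- S-033188: exp(−λ₁ × 298) − exp(−λ₁ × 336) = 0.163 − 0.130 = 0.034, about 13 of 395.

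**The case against.** The case on the other side is that nothing turns on this.

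- **Size.** The loss is 0.1 to 1.0 points. A simulation of 8,000 trials gave 89.2% at 336 h, 88.7% at 304 h and 88.1% at 286 h, so the planning formula itself is off by about 0.8 points before the diary is considered. An S-033188 median of about 113.5–113.7 h instead of 114 h would restore 90%. The protocol also calls its 36-hour difference conservative, and at 96 versus 150 h the power at 298 h is 99.9%. This all stands, and it limits the point to a small one.
- **A nominal figure.** The 336 hours appears only in the sample-size rationale and can be read as shorthand for a Day 1–14 diary. This stands only in part: the reproduction shows that 336 h was used as a numerical input, and the power claim depends on it.
- **Dating of the event.** Section 9.10.1 does not settle whether the time is the start or the end of the spell, and the analysis plan may do so. This stands, and is why both readings are shown. Neither reaches 336 h.

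A reader might infer that 286–304 h is a limit set by the protocol. It is not: it needs assumed clock times and dating to the start of the spell. A reader might also infer that losing late improvers endangers the comparison. Under the protocol's own model about 21% of placebo and 13% of S-033188 patients are still without improvement at 336 h. The further 4.1% and 3.4% are nearly balanced, and this test gives late events little weight.

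**Conclusion.** The inconsistency is real and its effect is minor. The diary ends before 336 h under any plausible dosing time: an entry at 24:00 on Day 14 reaches 336 h only if the dose was given at the very start of Day 1. The size of the gap, though not its existence, depends on the assumed clock times and on how the event is dated. It is about 32–50 h when dated to the start of the spell and 8–26 h when dated to the end.

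Under the protocol's exponential medians, power with 395 per arm is 89.0–89.4% or 89.6–89.9% respectively, against a stated minimum of 90% that is met at 336 h with nothing to spare. The claim is therefore narrowly missed. The documents do not support calling the trial underpowered in any practical sense. Both assumed medians lie well inside the window, and the primary test is not threatened.

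**What to change.** **Main change, Section 9.2.** Replace the 336-hour follow-up with the window that the diary can observe: about 300 h if the event is dated to the start of the 21.5-hour spell. Say which dating is meant and which clock times are assumed. Restate the power for 395 per arm as about 89%, and recompute Table 9-1 on the same basis. Over 286–304 h its last row becomes 89.6–89.8%. The cost is a slightly less favourable figure, with no change to conduct.

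**Optional alternative.** Extend the once-daily evening symptom entry to Day 16 in Section 7.4.1.2, Table 7-2 and Appendix 1 with footnote c. The last confirmable onset, dated to the start of the spell, becomes the Day 15 evening: 14 × 24 + (18:00 to 24:00) − (20:00 to 08:00) = 334–352 h. This is essentially the stated follow-up. It does not guarantee 336 h for every patient: a 20:00 dose with 18:00 entries still stops at 334 h. The cost is two more diary entries per patient and a device setting, with no extra visit.
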